11 DATA MONITORING COMMITTEES

11.1 Data Safety Monitoring Committee

An independent Data Safety Monitoring Committee (DSMC) will be convened for this study. The DSMC is an expert advisory group responsible for safeguarding the interests of trial participants and assessing the safety of the interventions during the trial. The DSMC will meet at intervals as specified in the DSMC charter and may convene for ad hoc meetings if there are immediate safety concerns identified during the study. Subject safety will be evaluated as specified in the DSMC charter. The DSMC will provide advice to the Sponsor and study Investigators as specified in the DSMC charter. The Sponsor will provide DSMC recommendations to the study Investigators for submission to the IRB/IEC per institutional policies, upon request.

11.2 Imaging Central Review

A blinded Imaging Central Review of the L3 vertebra Skeletal Muscle Index (SMI) and other muscle volume measures based on CT scans will be performed as specified in the Imaging Review Charter.

Confidential Page 50 of 64

12 STUDY GOVERNANCE

12.1 Regulatory and Ethical Conduct of the Study

This study will be conducted in accordance with the protocol and with the following:

- Consensus ethical principles derived from international guidelines including the Declaration of Helsinki and Council for International Organizations of Medical Sciences International Ethical Guidelines.
- Applicable ICH GCP Guidelines.
- Applicable local, federal or country-specific regulations and laws.

Prior to the onset of the study, the protocol, informed consent, and any other information to be provided to the subject must be approved by the IRB/IEC. Any amendments to the protocol, informed consent, or subject materials will require review and approval by the IRB/IEC before the changes are implemented to the study.

The Investigator will be responsible for:

- Obtaining continued review of the clinical research at intervals not exceeding 1 year or as otherwise specified by the IRB/IEC
- Notifying the IRB/IEC of SAEs or other significant safety findings as specified by the IRB/IEC procedures
- Providing oversight of the conduct of the study at the site and adherence to applicable guidelines and regulations
- Notifying the Sponsor in advance of an impending regulatory inspection. The
 Investigator may request that the Sponsor provide support for preparation, if necessary,
 and is required to provide updates on the ongoing activities during the inspection and
 submit any citations/objectionable findings (i.e., FDA 483) and is required to share any
 follow up responses to the outcome.

12.2 Financial Disclosure

Investigators, including sub-investigators, will provide the Sponsor with sufficient, accurate financial information as requested to allow the Sponsor to submit complete and accurate financial certification or disclosure statements to the appropriate regulatory authorities. Investigators are responsible for providing information on financial interests during the course of the study and for 1 year after completion of the study.

12.3 Informed Consent

The informed consent form (ICF) and any changes made to the ICF during the course of the study must be agreed to by the Sponsor or designee and the IRB/IEC prior to its use and must be in compliance with all ICH GCP, local regulatory requirements, and legal requirements.

Confidential Page 51 of 64

The Investigator or his/her representative will explain the nature of the study to the subject or his/her legally authorized representative (personal or professional, as applicable per local regulations) and answer all questions regarding the study.

Subjects must be informed that their participation is voluntary. Subjects or their legally authorized representative (personal or professional, as applicable per local regulations) will be required to sign a statement of informed consent that meets the requirements of 21 CFR 50, local regulations, ICH guidelines, Health Insurance Portability and Accountability Act requirements, where applicable, and the IRB/IEC or study center.

The medical record must include a statement that consent was obtained prior to the initiation of any study procedures and the date the consent was obtained. The Investigator or his/her representative obtaining consent must also sign the ICF.

A copy of the fully signed ICF(s) must be provided to the subject or the subject's legally authorized representative (personal or professional, as applicable per local regulations).

12.4 Data Protection

Each subject will be assigned a unique subject identification number by the Sponsor or designee that should be used on all forms associated with the subject's samples or documents that will be supplied to the Sponsor or designee or to any party processing the subject's samples or information on behalf of the Sponsor (e.g., samples for central laboratory analyses). Data privacy will be maintained according to applicable local, federal or country-specific regulations, laws or requirements and will not be released without the written permission of the subject (or the subject's legally authorized representative), except as necessary for monitoring and auditing by the Sponsor, its designee, the FDA or other applicable regulatory authority, or the IRB/IEC.

12.5 **Publication Policy**

The results of this study may be published or presented at scientific meetings in accordance with the provisions contained in the clinical trial agreement.

12.6 Dissemination of Clinical Study Data

The Sponsor will be responsible for ensuring the study information is appropriately listed and updated on the ClinicalTrials.gov website throughout the course of the study.

12.7 Data Quality Assurance

All subject data relating to the study will be recorded on the CRF unless transmitted to the Sponsor or designee electronically (e.g., central laboratory data). The Investigator is responsible for verifying that data entries are accurate and correct by signing the CRF.

The Investigator must maintain accurate documentation (source data) that supports the information entered in the CRF. Source documents provide evidence for the existence of the subject and substantiate the integrity of the data recorded. The Investigator may need to request previous medical records or transfer records. Also, current medical records must be available.

Confidential Page 52 of 64

Source documents are filed at the Investigator's site. Data entered in the CRF that are transcribed from source documents must be consistent with the source documents or the discrepancies must be explained.

The Investigator must maintain site files containing the protocol with all amendments and protocol signature pages, copies of all other required regulatory documentation, and all correspondence between the clinical trial site and the IRB and Sponsor or its designee.

The Investigator must maintain drug accountability files containing a complete account of the receipt and disposition of all study treatments.

The Investigator must maintain a subject identification list (subject and treatment numbers with the corresponding subject names) to enable records to be identified.

The Sponsor or designee is responsible for the data management of this study including quality checking of the data. Data will be processed using a validated computer system conforming to regulatory requirements. Data quality checks programmed within the EDC system, as well as supplemental data quality checks performed by review of the downloaded data, will be applied to ensure accurate, consistent, and reliable data. Data identified as potentially inaccurate or incomplete will be referred to the clinical trial site for resolution through data queries.

The Investigator must permit study-related monitoring, audits, IRB/IEC review, and regulatory agency inspections and provide direct access to source data documents and inform the Sponsor of any such inspection immediately.

Study monitors will perform ongoing source data verification to confirm that data entered into the CRF by authorized site personnel are accurate, complete, and verifiable from source documents; that the safety and rights of subjects are being protected; and that the study is being conducted in accordance with the currently approved protocol and any other study agreements, ICH GCP, and all applicable regulatory requirements. The Investigator will permit the Sponsor or their designee to monitor the study as frequently as deemed necessary to determine that data recording and protocol adherence are satisfactory. During the monitoring visits, information recorded on the CRFs will be verified against source documents and requests for clarification or correction may be made. The monitor will review the data for safety information, completeness, accuracy, and logical consistency.

The Sponsor or their designee may arrange a visit to the clinical trial site to audit the performance of the study and the study documents originating at the site. The Investigator will be informed of the outcome of the audit.

Records and documents, including signed ICFs, pertaining to the conduct of this study must be retained by the Investigator for 2 years following marketing application approval or investigation is discontinued by the Sponsor and regulatory authorities are notified unless local regulations or institutional policies require a longer retention period. No records may be destroyed during the retention period without the written approval of the Sponsor. No records may be transferred to another location or party without written notification to the Sponsor. Prior to transfer or destruction of these records, the Sponsor must be notified in writing and be given the opportunity

Confidential Page 53 of 64

to further store such records. If the Investigator relocates, retires, or for any reason withdraws from the study, the Sponsor should be prospectively notified. The study records must be transferred to an acceptable designee, such as another Investigator, another institution, or to the Sponsor.

12.8 Study and Site Closure

The Sponsor or designee reserves the right to close the clinical trial site or terminate the study at any time for any reason at the sole discretion of the Sponsor. In the event of such action, written notification documenting the reason for study termination will be provided to each Investigator. Additionally, the Sponsor or its designee will inform the appropriate regulatory authorities of the termination of the study and the reasons for termination, and the Investigator will inform the IRB/EC of the same. In terminating the study, the Sponsor and the Investigator will assure that adequate consideration is given to the protection of the subjects' interests. Circumstances that may warrant early termination include, but are not limited to:

- Discovery of an unexpected, serious or unacceptable risk to subjects enrolled in the study
- Evidence suggesting that safety risks associated with FDY-5301 outweigh the possible benefit for the subject or at recommendation of the DSMC
- Decision on the part of the Sponsor to suspend or discontinue testing of the study drug

Clinical trial sites will be closed upon study completion. A clinical trial site is considered closed when all required documents and study supplies have been collected and a study-site closure visit has been performed.

The Investigator may initiate study-site closure at any time, provided there is reasonable cause and sufficient notice is given in advance of the intended termination.

Reasons for the early closure of a clinical trial site by the Sponsor or Investigator may include but are not limited to:

- Failure of the Investigator to comply with the protocol, the requirements of the IRB/IEC or local health authorities, the Sponsor's procedures, or GCP guidelines
- Inadequate recruitment of subjects by the Investigator

Confidential Page 54 of 64

APPENDIX 2: CLINICAL LABORATORY TESTS

Biochemistry

Alanine aminotransferase	Glucose
Albumin	Inorganic phosphorus
Alkaline phosphatase	Lactate dehydrogenase
Aspartate aminotransferase transaminase	Potassium
Bicarbonate	Sodium
Blood urea nitrogen	Total and conjugated bilirubin
Chloride	Total protein
Total calcium	Uric acid
Creatinine	*TSH, free T3, and free T4
Gamma-glutamyl transferase	

^{*}TSH = thyroid stimulating hormone; T3 = triiodothyronine; T4 = thyroxine

Hematology

Hematocrit	Mean corpuscular volume
Hemoglobin	Platelets
Mean corpuscular hemoglobin	Red blood cell count
Mean corpuscular hemoglobin concentration	White blood cell count and differential (absolute neutrophils, lymphocytes, monocytes, eosinophils, and basophils)

Confidential Page 58 of 64

APPENDIX 3: TRISS METHOD

Variables	Severity level	Points
ISS		.
Head and Neck	none	0
	Minor	1
	Moderate	2
	Serious	3
	Severe	4
	Critical	5
	Maximum/unsurvivable	6
Face	none	0
	Minor	1
	Moderate	2
	Serious	3
	Severe	4
	Critical	5
	Maximum/unsurvivable	6
Chest	none	0
	Minor	1
	Moderate	2
	Serious	3
	Severe	4
	Critical	5
	Maximum/unsurvivable	6
Abdomen, pelvic contents	none	0
	Minor	1
	Moderate	2
	Serious	3
	Severe	4
	Critical	5
	Maximum/unsurvivable	6
Extremity, pelvic girdle	none	0
	Minor	1
	Moderate	2
	Serious	3
	Severe	4
	Critical	5
	Maximum/unsurvivable	6
External	none	0
	Minor	1
	Moderate	2

Confidential Page 59 of 64

	These was	I: 30
	Serious	3
	Severe	4
	Critical	5
	Maximum/unsurvivable	6
RTS	98	×
Respiratory rate (per min)	0	0
	1-5	1
	6-9	2
	10-29	4
	≥ 30	3
Systolic blood pressure (mmHg)	0	0
	1-49	1
	50-75	2
	76-89	3
	≥ 90	4
Glasgow Coma Scale	*	
Eye opening response	Spontaneous	4
	To verbal stimuli	3
	To pain only	2
	No response	1
Verbal response	Oriented	5
	Confused, but able to answer questions	4
	Inappropriate words	3
	Incomprehensible speech	2
	No response	1
Motor response	Obeys commands	6
	Purposeful movement to painful stimulus	5
	Withdraws in response to pain	4
	Flexion in response to pain (decorticate posturing)	3
	Extension in response to pain (decerebrate posturing)	2
	A. Carriera de la Carriera del Carriera de la Carriera del Carriera de la Carrier	
	No response	1
Age	No response < 55 years	0

Sources: Boyd C, Tolson M, Copes W. Evaluating trauma care: the TRISS method. Trauma Score and the Injury Severity Score. J Trauma Inj Infect Crit Care. 1987; 27:370–8.

Confidential Page 60 of 64

APPENDIX 4: ORGAN DYSFUNCTION TTR

Time to recovery (TTR) is defined as the first day of meeting the criteria for organ failure recovery in all systems listed below, without any subsequent days with further organ system failure.

Cardiovascular recovery

Mean arterial pressure >60 mmHg and no inotropic/vasopressor support (dopamine, dobutamine, epinephrine, norepinephrine, phenylephrine, or vasopressin)

Hematologic recovery

Platelet count >120,000/mL

Hepatic recovery

Serum bilirubin <3 mg/dL

Renal recovery

No dialysis and creatinine <1.3 mg/dL

Respiratory recovery

No mechanical ventilation or PaO₂/FiO₂ >300

FiO2 = fraction of inspired oxygen; PaO2 = partial pressure of arterial oxygen.

Source: Raymond SL, Hawkins RB, Wang Z, et al. Prospective Validation of a Transcriptomic Metric in Severe Trauma. Ann Surg. 2019 Jan 24. doi: 10.1097/SLA.0000000000003204. (Epub ahead of print)

Confidential Page 61 of 64

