- Medical Outcomes Study Questionnaire Short Form 36v2 Health Survey (SF-36v2) and activities of daily living questionnaire (Barthel Index) at Day 28 or hospital discharge (whichever occurs first), Month 3, and Month 6
- Proportion of subjects who can complete any sit-tostand maneuver and the number of sit-to-stand maneuvers completed in 30 seconds at Days 10, 14, 21, and Day 28 or hospital discharge, whichever occurs first
- Individual organ dysfunction TTR until Day 28

In a subset of subjects:

- Blood metabolic, inflammatory, and biochemical markers of muscle damage analysis at Days 1, 3, and 7
- Plasma iodide concentrations evaluated up to 4 hrs pre- and post-dose on Days 1, 3, and 7
- Leukocyte gene expression analysis at Days 1 and 7
- Percent change from baseline in the level of the 3rd lumbar (L3) vertebra Skeletal Muscle Index (SMI) and other muscle volume measures based on Computerized Tomography (CT) scan at Day 10

[figure not shown]
Confidential Page 23 of 64

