6.1.3 Organ Dysfunction Time to Recovery (TTR)

Organ dysfunction time to recovery (TTR) will be assessed based on the criteria presented in Appendix 4: Organ Dysfunction TTR. The definition of time to recovery is the first day meeting the organ failure recovery criteria in cardiovascular, hematologic, hepatic, renal, and respiratory systems without any subsequent days with further organ system failure.

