6.2.7 Safety Laboratory Tests

Clinical laboratory evaluations will be performed by each site's clinical laboratory per institutional guidelines. See Appendix 2: Clinical Laboratory Tests for a list of required analytes. Additional assessments may be performed between scheduled study visits as clinically required to diagnose and monitor AEs/SAEs.

6.2.8 12-Lead Electrocardiogram

Standard 12-lead ECGs will be performed as single recordings and read at the clinical site.

Confidential Page 36 of 64

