10.2.4.1 Primary Efficacy Analyses

There are two co-primary efficacy endpoints defined in this study:

- CPAx total score at Day 10 (or at hospital discharge, whichever occurs first)
- Organ dysfunction total TTR until Day 28

Both primary endpoints will be compared across treatment groups and tested at the 0.05 level of significance and, by convention, both endpoints must demonstrate statistical significance (i.e., $p \le 0.05$) to conclude treatment superiority for regulatory purposes.

For the first primary efficacy endpoint, CPAx total score at Day 10 (or at hospital discharge, whichever occurs first), the following hypothesis will be tested:

$$H_0$$
: $\mu_{Tp} = \mu_p \ v. s. H_a$: $\mu_{Tp} \neq \mu_p$

Where μ_{Tp} , μ_p denote the CPAx total score at Day 10 (or at hospital discharge, whichever occurs first) in the pooled treatment group (FDY-5301 1 mg/kg and FDY-5301 2 mg/kg combined) and placebo groups, respectively. As the primary analysis, the treatment comparison of the CPAx total scores will be performed using analysis of covariance (ANCOVA). The model will include CPAx total score at Day 10 (or at hospital discharge, whichever occurs first) as dependent variable treatment and stratification category (with or without presence of pelvic or lower limb fractures) as factors; and "baseline" CPAx (the first available datapoint) as a continuous covariate.

The p-values, least-squares means, standard errors, and the 2-tailed 95% confidence intervals for the treatment groups and placebo group will be presented.

Confidential Page 47 of 64

If the difference between the means of the pooled treatment group compared to the placebo group is statistically significant, a step-down procedure will be followed to test the individual FDY-5301 doses compared to placebo. The following testing order of doses will be used:

- 1) FDY-5301 2 mg/kg versus placebo
- 2) FDY-5301 1 mg/kg versus placebo

The same statistical method as for the comparison between the pooled treatment group and placebo will be used.

For the second primary efficacy endpoint, organ dysfunction total TTR, the time will be calculated as date of recovery minus date of treatment start plus 1 day. The time to recovery will be estimated using Kaplan-Meier methodology. The Kaplan-Meier curves will be plotted and the time to recovery will be compared using log-rank test at significance level 0.05. The pooled versus placebo and then step-down analysis procedure will be used.

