APPENDIX 5: SOFA CRITERIA

SOFA Score	0	1	2	3	4
Respiration	>400	301 - 400	201 - 300	101 - 200	≤100
PaO ₂ /FiO ₂				With	With
				respiratory	respiratory
				support	support
Coagulation	>150	101 - 150	51 - 100	21-50	≤20
Platelets, $x10^3/mm^3$					
Liver					
Bilirubin, mg/dL	<1.2	1.2 - 1.0	2.0 - 5.9	6.0 - 11.0	>12.0
(µmol/L)	(<20)	(20 - 32)	(33 - 101)	(102 - 204)	(>204)
Cardiovascular	MAP ≥70	MAP<70	Dopamine	Dopamine>5	Dopamine>15
Hypotension	mmHg	mmHg	\leq 5 or	or epinephrine	or
			dobutamine	≤0.1 or	epinephrine>0.1
			(any dose)*	norepinephrine	or
				≤0.1*	norepinephrine
63.12		10 11	10 10	6 0	>0.1*
CNS	15	13 - 14	10 - 12	6 - 9	<6
Glasgow Coma					
Score					
Renal					
Creatinine,	<1.2	1.2 - 1.9	2.0 - 3.4	3.5 - 4.9	>5.0
mg/dL	(<110)	(110 - 170)	(171 - 299)	(300 - 440)	(>440)
(µmol/L)				Or <550mL/d	Or <200mL/d
Or urine output					

CNS = central nervous system; d = day; FiO_2 , fractional inspired oxygen; MAP, mean arterial pressure; PaO_2 , partial arterial oxygen pressure.

a Adrenergic agents administered for at least 1 hour (doses are given in µg/kg/min).

Source: Vincent JL, Moreno R, Takala J, Willatts S, De Mendonca A, Bruining H, Reinhart CK, et al. The SOFA (Sepsis-related Organ Failure Assessment) score to describe organ dysfunction/failure. Working Group on "sepsis-related problems" of the European Society of Intensive Care Medicine. Intensive Care Med 1996;22:707-710.

Confidential Page 62 of 64

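### Appendix 4 prints the platelet threshold for the co-primary TTR per mL, which is 1,000 times lower than the same number per mm³; the unit needs to be checked and stated once

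*Combined protocol and SAP*

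**What the plan says.** Section 6.1.3 says that organ dysfunction TTR "will be assessed based on the criteria presented in Appendix 4". It names five systems that must all have recovered: cardiovascular, hematologic, hepatic, renal and respiratory.

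Appendix 4 gives the hematologic criterion as "Platelet count >120,000/mL". In the same list, the hepatic criterion is "Serum bilirubin <3 mg/dL" and the renal criterion is "No dialysis and creatinine <1.3 mg/dL". No other part of the text reviewed gives a platelet threshold or a platelet unit for TTR.

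Appendix 5 labels its SOFA coagulation row "Platelets, $x10^3/mm^3" (the stray symbols come from text conversion). The bands are above 150 for grade 0, 101–150 for grade 1, 51–100 for grade 2, 21–50 for grade 3, and 20 or below for grade 4.

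On the role of the endpoint, Section 10.2.4.1 requires that "both endpoints must demonstrate statistical significance". Section 2 also lists "Individual organ dysfunction TTR until Day 28" as exploratory. Section 6.2.7 has laboratory tests done by each site's "clinical laboratory per institutional guidelines", and Appendix 2 lists platelets without a unit. Section 10 leaves further detail to a separate SAP, which is not in the text reviewed.

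**The concern.** The same quantity appears on two scales in adjacent appendices, and the scales do not fit together. Read as printed, a platelet count deep inside the worst SOFA coagulation grade already satisfies hematologic recovery for TTR.

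If a programmer or a site took the printed unit at face value, the hematologic component would be met by practically every subject on every assessed day. The co-primary endpoint would then record recovery from four organ systems rather than five, and the separate hematologic TTR would be close to constant. A definition on which the primary conclusion depends should not need the reader to correct it by a factor of 1,000.

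**Working it through.** **Inputs.** Recovery threshold: above 120,000 per mL (Appendix 4). SOFA platelet bands in ×10³/mm³ (Appendix 5). Conversion: 1 mL = 1,000 mm³, and 1 mm³ = 1 microliter.

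**Step 1: convert the printed threshold.**
120,000 per mL ÷ 1,000 = 120 per mm³ = 0.12 ×10³/mm³.

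**Step 2: compare with the same numeral per mm³.**
120,000 per mm³ = 120 ×10³/mm³. Ratio: 120 ÷ 0.12 = 1,000.

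**Step 3: place the threshold on the SOFA scale.**
Top of grade 4 ÷ printed threshold = 20 ÷ 0.12 = 166.7. Every count above 0.12 and up to 20 is both grade 4 and hematologic recovery as printed.

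| Count (×10³/mm³) | SOFA grade | Recovered, per mL as printed | Recovered, same numeral per mm³ |
|---|---|---|---|
| 0.1 | 4 | no | no |
| 5 | 4 | yes | no |
| 20 | 4 | yes | no |
| 35 | 3 | yes | no |
| 75 | 2 | yes | no |
| 110 | 1 | yes | no |
| 121 | 1 | yes | yes |
| 200 | 0 | yes | yes |

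The last column is for comparison only. The documents do not confirm that unit.

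**Step 4: ask how much weight the SOFA overlap can bear.** TTR and SOFA are different instruments and need not share cut-offs.

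- Bilirubin below 3 mg/dL can score SOFA 2 (band 2.0–5.9).
- Creatinine below 1.3 mg/dL can score 1 on creatinine (band 1.2–1.9).
- Mean arterial pressure above 60 mmHg without vasopressors can score 1 (below 70).
- The renal recovery criterion ignores urine output, so it can be met with output below 200 mL/d, which is SOFA renal grade 4.
- The respiratory criterion is met off mechanical ventilation at any PaO₂/FiO₂. If respiratory support in SOFA includes support other than a ventilator, recovery can coexist with grade 3 or 4.

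Overlap with a high SOFA grade is therefore not unique to platelets. What the overlap does show is that the printed platelet unit is implausible as a recovery threshold.

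**Step 5: check whether the design figures depend on the unit.** Section 10.2.7 gives medians of 7 and 4.9 days, 213 events and about 70% power. The ratio is 4.9 ÷ 7 = 0.70, and pooled active versus placebo is 2:1. With Schoenfeld's formula:

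√(213 × 1/3 × 2/3) × |ln 0.70| − 1.960 = 6.880 × 0.3567 − 1.960 = 0.494, and Φ(0.494) = 0.689.

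This agrees with the stated 70%. The platelet unit does not enter the calculation.

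**The case against.** The strongest objection is that the letter before L may be a micro sign lost when the PDF was read. The abbreviation list defines microliter, yet the text reviewed uses it nowhere else, and the platelet line is a natural place for it. The neighbouring appendices also look damaged: in Appendix 5, bilirubin grade 1 reads 1.2 to 1.0, an impossible range. Against this, the micro sign survives in the abbreviation list, in Section 7.4 and in the footnote to Appendix 5, and the list holds other entries, such as A-aDO₂, that are not used elsewhere either. Neither side settles it. The objection stands far enough to make the source page the first check and to hold confidence at medium.

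A second objection is that laboratories and programmers will use a conventional scale whatever Appendix 4 prints, since Appendix 5 shows one. That may well be so. The documents do not show it, because the SAP, CRF and derivation code are not available.

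A reader might also infer that platelets are the only criterion for which recovery can coexist with a worst SOFA grade. The documents do not support that, as the urine output and respiratory items show.

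Nor do they support the inference that the printed unit would certainly disable reversal of recovery. Appendix 4 requires that no later day show further organ system failure but does not define failure. Only if failure means not meeting the recovery criterion would the threshold also govern reversal.

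**Conclusion.** The point holds as a unit that is wrong as printed, in the governing definition of a co-primary endpoint, subject to the source page. The discrepancy is a factor of 1,000 (0.12 against 120 ×10³/mm³ for the same numeral). Applied literally, the platelet criterion would almost never delay recovery. This assumes that counts at or below 0.12 ×10³/mm³ practically do not occur. The documents give no distribution of counts, but the assumption is mild given that the worst SOFA grade already begins at 20.

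A reader might go further and infer lost power, inflated type I error or bias between arms. The documents support none of these: the stated power does not depend on the unit, the same definition applies to every arm, and the other four systems still govern TTR. The size of any effect on TTR cannot be derived from the documents. It is also not shown that anyone has used, or will use, the printed unit.

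The point should be fixed because the endpoint is co-primary and the correction is small. Confidence is medium, limited by the possible reading artefact.

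**What to change.** 1. Check the source page of Appendix 4. If it prints per microliter, drop the point.
2. If per mL stands, reconcile the platelet unit in Appendix 4 with the unit in Appendix 5 and with the cited source of the recovery criteria, and state the unit once.
3. Before unblinding, confirm that the SAP, the CRF and the TTR derivation use that unit.
4. If data have already been collected, re-derive recovery dates where platelet counts were recorded. Table 1 schedules post-baseline safety laboratory tests on Days 3, 7, 14, 21 and 28 (or discharge), whereas TTR is assessed on Days 1 to 7, 10, 14, 21 and 28. The text reviewed does not show that a count is held for every TTR day, so the re-derivation should report how many days lack one.

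The cost is one unit in one appendix and a check of the specifications. No new assessments are needed.
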